6.7.6.2. Severity Assessment

Adverse events will be classified by the Investigator using the National Cancer Institute (NCI) Common Terminology Criteria for Adverse Events (CTCAE), version 5.0. All appropriate treatment areas should have access to a copy of the CTCAE version 5.0. A copy of the CTCAE version 5.0 can be downloaded from the Cancer Therapy Evaluation Program website (<http://ctep.cancer.gov>). If the CTCAE grade is not specified for a particular event or if the event term does not appear in the CTCAE, general guidelines for grading severity of AEs are provided in [Table 5](#). When the severity of an AE increases over time, the increase in the severity will be recorded as a new AE and the original AE will stop when the new AE starts except in the following scenario.

Cohort 1 (Part A and Part B): From the time written informed consent is obtained through completion of Course 1, when the severity of an AE changes over time, the decreases and increases in severity will be recorded as a new AE, and the original AE will stop when the new AE starts.

The CTCAE should be used for severity assessment only; it is not intended for use in event term selection (see [Section 6.7.6.1](#) for AE terminology).

Table 5: CTCAE Severity Grades General Guidelines v5.0

Grade 1	Mild; asymptomatic or mild symptoms; clinical or diagnostic observations only; intervention not indicated.
Grade 2	Moderate; minimal, local or noninvasive intervention indicated; limiting age-appropriate instrumental activities of daily living (ADL) ^a .
Grade 3	Severe or medically significant but not immediately life-threatening; hospitalization or prolongation of hospitalization indicated; disabling; limiting self-care ADL ^b .
Grade 4	Life-threatening consequences; urgent intervention indicated.
Grade 5	Death related to AE.

^a Instrumental ADL refers to preparing meals, shopping for groceries or clothes, using the telephone, managing money, etc.

^b Self-care ADL refers to bathing, dressing and undressing, feeding self, using the toilet, taking medications, and not bedridden.

Note: A semi-colon indicates 'or' within the description of the grade.

Abbreviations: ADL=activities of daily living; AE=adverse event; CTCAE=Common Terminology Criteria for Adverse Events.

Source: CTCAE v5.0 accessed at:

https://ctep.cancer.gov/protocolDevelopment/electronic_applications/docs/CTCAE_v5_Quick_Reference_8.5x11.pdf
https://ctep.cancer.gov/.../electronic.../docs/CTCAE_v5_Quick_Reference_8.5x11.pdf

6.7.6.3. Serious Adverse Events (SAEs)

An SAE is an AE that fulfills any of the following criteria, as per International Council on Harmonisation (ICH) E2A.II.B:

- Is fatal (results in death).
- Is life-threatening (Note: The term “life-threatening” refers to an event in which the patient was at immediate risk of death at the time of the event; it does not refer to an event that could hypothetically have caused death had it been more severe. Grade 4 laboratory values are not necessarily serious unless the patient was at immediate risk of death.).
- Requires inpatient hospitalization or prolongs existing hospitalization.
- Results in persistent or significant incapacity or disability, defined as substantial disruption of the ability to conduct normal life functions.
- Results in a congenital anomaly/birth defect.
- Is an important medical event.
 - Important medical events that may not result in death, be life-threatening, or require hospitalization may be considered an SAE when, based on appropriate medical judgment, they may jeopardize the patient and may require medical or surgical intervention to prevent one of the outcomes listed above in the definition of an SAE.

- Examples of such medical events include allergic bronchospasm requiring intensive treatment in an emergency room or at home, blood dyscrasias or convulsions that do not result in inpatient hospitalization, the development of drug dependency or drug abuse.
- Additionally, any suspected transmission of an infectious agent via a medicinal product is considered an important medical event.

An AE should be recorded as an SAE when it meets at least one of the criteria for seriousness. A patient's underlying disease that results in the initial hospitalization is not considered an SAE. The following reasons for hospitalization are also NOT considered SAEs:

- Procedures that were planned prior to the patient entering the study.
- Social reasons and respite care in the absence of any deterioration in the patient's general condition.
- Procedures that are elective in nature and not related to worsening of an underlying condition.

Complications that occur during hospitalizations are AEs. If a complication prolongs the hospitalization, it is an SAE.

"Inpatient hospitalization" means the patient has been formally admitted to a hospital for medical reasons, for any length of time. Emergency room care without admission to a hospital is considered outpatient care.

6.7.6.4. Causal Relationship to Study Drug

The Investigator's assessment of the relationship of the AE to study drug (ie, RC-P) is required. The relationship or association of the study drug in causing or contributing to the AE will be characterized using the following classification and criteria:

Related to Study Drug	
There is a reasonable possibility that the study drug caused the event—ie, there is evidence to suggest a causal relationship between the study drug and the AE.
 
Some temporal relationship exists between the event and the administration of the study drug and the event is unlikely to be explained by the patient's medical condition, other therapies, or accident.
 
The event follows a reasonable temporal sequence from administration of the study drug and at least 1 of the following instances of clinical evidence:
 
 • The event follows a known or suspected response pattern to the study drug. • The event improves upon stopping the study drug or decreasing the dose (positive dechallenge). • The event reappears upon repeated exposure, if medically appropriate (positive rechallenge).
-----------------------	--

RC-P
Protocol Amendment 02: JZP458-201

Jazz Pharmaceuticals Ireland Limited

Not Related to Study Drug	
There is not a reasonable possibility or clinical evidence that the study drug caused the event.
 
The event can be readily explained by other factors such as the patient's underlying medical conditions, concomitant therapy, or accident; or there is no temporal relationship between study drug and the event.

---------------------------	--

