Part A Cohort 2 (IM Expansion): Approximately 85 patients are expected to be enrolled in this cohort and each patient is planned to receive at least 6 doses (1 course) of IM RC-P at the final IM RC-P dose level selected from Part A Cohort 1.

As described for Cohort 1, Cohort 2 patients will also have the 6 IM RC-P doses administered on a MWF schedule over 2 weeks with the initial dose starting either on a Monday or Wednesday or Friday (depending on the patient's planned chemotherapy schedule). Blood samples for SAA level determination for patients in Part A Cohort 2 will be collected as described under PK assessments (Section 6.4). Safety will be assessed in Part A Cohort 2 by monitoring for and characterizing AEs.

The SDRC will review the data on NSAA levels at frequent intervals for Cohort 2 (see Section 9.6); these reviews will occur when totals of 19, 32, and 51 patients (Cohort 1 plus Cohort 2 at the final IM RC-P dose with $n = 51$ as the interim analysis) complete Course 1. In addition, the SDRC will review the data to assess the safety of the selected dose level when 32 and 51 patients complete Course 1. Enrollment for this cohort may be stopped if the incidence of allergic reactions (including hypersensitivity and anaphylaxis) related to RC-P exceeds 25%, or the incidence of pancreatitis exceeds 10%, or thrombosis exceeds 10%.

An interim analysis is planned after the 51st patient completes Course 1 with the final IM RC-P dose level (Cohort 1 plus Cohort 2 patients). If the primary endpoint is met (ie, the lower bound of 95% Wald CI for the primary efficacy endpoint exceeds 90%) at the interim analysis, the enrollment to this cohort will be stopped early for efficacy. If the incidence of allergic reactions (including hypersensitivity and anaphylaxis) related to RC-P exceeds 25%, or the incidence of pancreatitis exceeds 10% or thrombosis exceeds 10% at this interim analysis, enrollment into this IM Expansion Cohort may be stopped for safety. If enrollment to this cohort is stopped early, other doses or schedules with RC-P could be considered.

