5.2. Study Treatment Dosages

Dosages (mg/m^2) will be administered based on the patient's body surface area (BSA), and calculated using the patient's height and weight taken prior to the start of each course. For institutions where BSA is not calculated by an existing algorithm in the electronic medical record (EMR), the calculation of BSA should be performed using the Mosteller formula as follows:

Metric units:
$$\text{BSA (m}^2\text{)} = ([\text{Height (cm)} \times \text{Weight (kg)}] / 3600)^{1/2}$$

Non-metric units (US):
$$\text{BSA (m}^2\text{)} = ([\text{Height (in)} \times \text{Weight (lb)}] / 3131)^{1/2}$$

Patients will receive doses of either RC-P via the IM or IV route depending on whether they are enrolled in Part A (IM) or Part B (IV) of the study. All other chemotherapy will continue according to the therapeutic regimen as defined in the patient's original treatment protocol for the patient's ALL/LBL. Intra-patient dose escalation may be permitted to the next dose level, if applicable, as recommended by the SDRC following review of a dose level.

IM RC-P Dose Confirmation (Part A):

In Part A of the study, RC-P will be administered via the IM route (prepared and administered as described in Study Pharmacy Manual). For **IM RC-P Dose Cohort 1**, the starting dose of RC-P will be $25 \text{ mg}/\text{m}^2$ (see [Section 1.4](#) for justification) with 6 IM RC-P doses administered on a MWF schedule over 2 weeks with the initial dose starting either on a Monday or Wednesday or Friday depending on the patient's planned chemotherapy schedule. [Appendix 1](#) provides the RC-P dosing schedule by the dose start day (Monday, Wednesday, and Friday). Additional IM RC-P cohorts may be enrolled based on the criteria in [Section 3.1.3.1](#) as determined by the Sponsor with guidance from the SDRC. The amount a dose may be increased is also described in [Section 3.1.3.1](#).

For IM administration, the volume of RC-P at a single injection site should be limited to 2 mL with the use of multiple injection sites if needed.

IV RC-P Dose Confirmation (Part B):

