6.7.6.5. Adverse Event Recording and Reporting

The Investigator must record all AEs that occur from the time written informed consent is obtained until 30 days after the patient's last dose of the last course of RC-P, regardless of their relationship to study drug.

In addition, any SAE assessed as related to study drug by the Investigator that occurs more than 30 days after the patient's last dose of the last course of RC-P, must be reported as described below.

Serious AEs must be reported to the Sponsor or its designee using an SAE Reporting Form within 24 hours of first knowledge of the event by study site personnel. The reporting form and contact information for submission of the form, will be provided to the study sites separately.

The reporting form must be completed as thoroughly as possible before transmittal to the contact provided on the form. The Investigator must provide his/her assessment of causality to the study drug and study procedure at the time of an initial SAE report. If the Investigator's assessment of causality changes after the initial report, it must be provided as follow-up information to the Sponsor.

Other Reportable Experiences:

Overdose, (defined as any dose administered or received that was higher than the intended dose), medication errors (defined as any unintentional error in the dispensing or administration of the study drug), and misuse of the study drug are considered reportable experiences and should be reported by study site personnel on an Other Reportable Experience Form. The form, and contact information for submission of the form, will be provided to the study sites separately.

If any overdose, medication error or misuse of the study drug results in an AE this must be recorded, and if this AE is serious it must also be reported as described above.

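### Protocol 6.7.6.4 gives conflicting tests for relatedness, so an event to which RC-P plausibly contributed can be recorded as not related and drop out of the related-only safety counts

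*Protocol*

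**What the plan says.** Protocol 6.7.6.4 (Causal Relationship to Study Drug) sets the investigator's task as characterizing "The relationship or association of the study drug in causing or contributing to the AE". It offers two categories.

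- **Related.** The heading reads "There is a reasonable possibility that the study drug caused the event". Two paragraphs follow. The first (call it a) asks for some temporal relationship and that "the event is unlikely to be explained by the patient's medical condition, other therapies, or accident". The second (b) asks for a reasonable temporal sequence plus at least one item of clinical evidence: positive dechallenge, positive rechallenge, or "The event follows a known or suspected response pattern to the study drug". No *and* or *or* joins a to b.
- **Not Related.** The heading denies a reasonable possibility, or clinical evidence, that the drug caused the event. The text beneath admits an event on this ground: "The event can be readily explained by other factors such as the patient's underlying medical conditions, concomitant therapy, or accident". Absence of a temporal relationship is the other ground.

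The background is multi-agent treatment. Protocol 5.2 states "All other chemotherapy will continue according to the therapeutic regimen", and 5.8.1 says the same.

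Relatedness is then used elsewhere. Protocol 3.1.1 says "Enrollment for this cohort may be stopped if the incidence of allergic reactions (including hypersensitivity and anaphylaxis) related to RC-P exceeds 25" per cent. The pancreatitis and thrombosis limits in the same sentence carry no relatedness condition. Protocol 6.7.6.5 extends reporting to "any SAE assessed as related to study drug by the Investigator that occurs more than 30 days after" the last dose. SAP 10.2 takes relatedness from a yes/no eCRF question and tabulates treatment-related TEAEs beside all TEAEs.

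**The concern.** The lead-in and the Related heading would call an event related if RC-P plausibly contributed. Paragraph a and the Not Related text look instead at whether something else could explain it. When every patient has ALL or LBL and continues chemotherapy, a competing explanation will often be on offer. The SAP's hypersensitivity term list (Appendix II) includes broad terms such as rash, dermatitis, bronchospasm and shock, for which an investigator could point to another drug. A shared-cause event then has no clear home, and the two phrases that create the conflict both lean toward Not Related.

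Four outputs are exposed: the treatment-related TEAE tables, the allergic-reaction incidence compared with the 25% limit, SAE reporting after day 30, and the length of follow-up under 6.7.6.6. Under that last section, unrelated events may be closed at the final visit or once otherwise explained, while related events are followed for as long as needed.

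**Working it through.** **1. One event put through each test.** Take an event that follows RC-P in time, fits a known asparaginase pattern, and could also readily be explained by a concomitant drug.

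| Text in 6.7.6.4 | Result |
|---|---|
| Lead-in (causing or contributing) | within scope |
| Related, heading | met |
| Related, paragraph a | not met |
| Related, paragraph b | met |
| Not Related, heading | not met |
| Not Related, supporting text | met |

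If a and b are both needed, the event fails Related despite meeting its heading. If they are alternatives, it is Related through b, yet it still meets the supporting text of Not Related. The eCRF answer is yes or no, and no tie-break is given. Either recording can be defended from the text.

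**2. What depends on the answer.**

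- *Depends:* treatment-related TEAE summaries (SAP 10.2); allergic reactions counted against 25% (Protocol 3.1.1, SAP 5.5); post-day-30 SAE reporting (Protocol 6.7.6.5); duration of follow-up (6.7.6.6).
- *Does not depend:* the primary safety endpoint, which is all TEAEs (Protocol 2.2.1); the summaries of adverse events of special interest (AESIs), found by preferred term with no relatedness filter stated (SAP 10.2.1); the 10% limits for pancreatitis and thrombosis.

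**3. The plan's nearest figure.** Protocol 8.3 gives the chance of seeing at least one asparaginase-related AE of 3% incidence as 95% with 98 patients and 79% with 51. Both reproduce: 1 − 0.97^98 = 0.9495 and 1 − 0.97^51 = 0.7885. The plan gives no figure for the 25% limit or for misattribution.

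**4. Illustration for the 25% limit.** The safety reviews are at 32 and 51 patients.

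- 0.25 × 32 = 8, so exceeding the limit takes 9 of 32 (28.1%).
- 0.25 × 51 = 12.75, so it takes 13 of 51 (25.5%).

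Let p be the true incidence of allergic reactions that RC-P caused or contributed to, and q the share of them recorded as not related. Neither is in the documents. I assume p = 0.30 and q from 0 to 0.30. The recorded count is then binomial with rate p(1 − q).

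| q | p(1 − q) | P(at least 9 of 32) | P(at least 13 of 51) | True reactions among 51 for 13 recorded, 13/(1 − q) rounded up |
|---|---|---|---|---|
| 0 | 0.30 | 0.656 | 0.802 | 13 |
| 0.10 | 0.27 | 0.510 | 0.648 | 15 |
| 0.20 | 0.24 | 0.355 | 0.455 | 17 |
| 0.30 | 0.21 | 0.215 | 0.262 | 19 |

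The true incidence that shows as exactly 25% is 0.25/(1 − q): 27.8%, 31.3% and 35.7% for q = 0.10, 0.20 and 0.30. If q is near zero, the first row applies and nothing changes.

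**The case against.** The strongest reply is that paragraph b is a sufficient alternative. Each paragraph states its own temporal condition, which fits alternatives better than one cumulative test. Allergic reactions are named as asparaginase events in Protocol 1.3 and 6.7.8, so a typical one meets b without chemotherapy being ruled out. The Not Related heading also excludes any event with a reasonable possibility of RC-P causation. On this reading the lost share could be close to zero. That is a fair reading and it stands as a possibility. But the protocol never states it, and even then the supporting text of Not Related still admits the same event.

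Safeguards also exist. All AEs are recorded whatever their cause, and SAP 10.2 sets all-cause tables beside related ones. Missing relatedness counts as related, and repeat events take the closest relationship. Events that lead to discontinuation are followed at length regardless of relatedness. The 25% rule is discretionary. These points limit the damage, but the missing-data rule does not help once an investigator has answered no.

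A reader might infer more than the documents support:

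- *That the definition requires other therapies to be ruled out.* That is one of two readings.
- *That related rates are in fact understated.* The documents give no misattribution rate, so only the possibility and its likely direction are shown.
- *That the 25% limit itself is understated, or that the pancreatitis and thrombosis limits are affected.* The limit is fixed and only the incidence counted against it can move; the other two limits do not use relatedness.
- *That a single-arm study leaves any loss invisible.* The gap between all-cause and related counts will show in the tables, though not which of the unrelated calls were wrong.

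**Conclusion.** The conflict in 6.7.6.4 is real and can be seen from the text alone. A shared-cause event can satisfy both categories, and the treatment-related rates, the allergic incidence counted against 25%, late SAE reporting and follow-up can be understated or curtailed as a result. The size cannot be determined from the documents. It ranges from about nothing, if sites treat the known-response-pattern paragraph as sufficient, to the illustrated fall from 80% to between 65% and 26% in the chance of exceeding 25% at 51 patients. That illustration rests on an assumed 30% true rate, an assumed 10% to 30% loss, and errors in one direction only. The main safety results do not depend on relatedness, so this is a correction worth making rather than a threat to the study's conclusions.

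**What to change.** In Protocol 6.7.6.4:

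1. Define Related as a reasonable possibility that RC-P caused or contributed to the event.
2. State that the two supporting paragraphs are alternatives.
3. State that another plausible cause does not by itself make an event not related.
4. Align the Not Related text with its own heading, so that it covers only events with no reasonable possibility of an RC-P role.

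At the 32- and 51-patient reviews, show allergic-reaction incidence regardless of relatedness beside the related-only figure. The SAP's AESI term lists already supply the definition. The enrollment rule itself need not change for this.

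The cost is protocol and eCRF-guideline wording and a notice to sites. Treatment-related rates would probably come out somewhat higher, hence less favourable. All-cause results would not change.

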6.7.6.5. Adverse Event Recording and Reporting

The Investigator must record all AEs that occur from the time written informed consent is obtained until 30 days after the patient's last dose of the last course of RC-P, regardless of their relationship to study drug.

In addition, any SAE assessed as related to study drug by the Investigator that occurs more than 30 days after the patient's last dose of the last course of RC-P, must be reported as described below.

Serious AEs must be reported to the Sponsor or its designee using an SAE Reporting Form within 24 hours of first knowledge of the event by study site personnel. The reporting form and contact information for submission of the form, will be provided to the study sites separately.

The reporting form must be completed as thoroughly as possible before transmittal to the contact provided on the form. The Investigator must provide his/her assessment of causality to the study drug and study procedure at the time of an initial SAE report. If the Investigator's assessment of causality changes after the initial report, it must be provided as follow-up information to the Sponsor.

Other Reportable Experiences:

Overdose, (defined as any dose administered or received that was higher than the intended dose), medication errors (defined as any unintentional error in the dispensing or administration of the study drug), and misuse of the study drug are considered reportable experiences and should be reported by study site personnel on an Other Reportable Experience Form. The form, and contact information for submission of the form, will be provided to the study sites separately.

If any overdose, medication error or misuse of the study drug results in an AE this must be recorded, and if this AE is serious it must also be reported as described above.

6.7.6.6. Follow-up of Adverse Events

All AEs and SAEs assessed as not related to study drug, including clinically significant laboratory tests, or physical examination findings, must be followed until the event resolves, the condition stabilizes, the event is otherwise explained, or the final study visit occurs, whichever comes first.

Adverse events and SAEs assessed as related to study drug, and AEs and SAEs resulting in discontinuation of study drug or study termination should be followed for as long as necessary to adequately evaluate the patient's safety, or until the event stabilizes, or the patient is lost to follow up. If the event resolves during the study, a resolution date should be recorded, for both AEs and SAEs. If at the time of the final scheduled study visit, the AE is not resolved, the

outcome at that time should be recorded. Once the final outcome is determined for an SAE this information should be provided as follow-up SAE information.

The Investigator is responsible for ensuring that follow-up includes any supplemental investigations indicated to elucidate the nature and/or causality of the event. This may include additional clinical laboratory testing or investigations, examinations, histopathological examinations, or consultation with other health care professionals as is practical, according to Jazz Pharmaceuticals' requests.

The Investigator should provide follow-up SAE information for any updates to information previously provided to Jazz Pharmaceuticals.

